7.1.4.12 Percentage of days with intake of COPD rescue therapy

Patients will complete the EXACT-PRO starting from Study Day 1 and will record rescue medication use and any occurrences of COPD once a day (evening) in the diary. The percentage of days with intake of rescue medications will be evaluated on the basis of the information recorded daily by the patient on the diaries.

A day will be considered with intake of rescue medications if the answer to the question “How many puffs of rescue medication did you take since last evening?” is > 0.

Inter-Visit Period:

For the calculation of the percentage of days, the inter-visit periods are defined as below:

Inter-visit period visit i - visit $i+1$ ($1 \leq i \leq 11$)	
Date of start of the period	Date of end the period

 If $i=1$ then date of start = date of Study Day 1. Else date of start = date of visit i. 	
 If visit i is NOT the last clinic visit performed before the End of Study then date of end = date of visit $i+1$ - 1 day (i.e., the day before visit $i+1$). Else date of end = date of End of Study. This includes the case date of visit $i+1$ = date of End of Study.

On a per patient basis, the percentage of days in each inter-visit period will be calculated using the following formula:

- % of days with rescue medication (inter-visit period) = (Number of days with rescue medication during the inter-visit period / Number of days with data recorded during the inter-visit period)*100.

Acute Exacerbation Phase:

- Percentage of days: data recorded from Study Day 1 to the day before Visit 9/Day 14 will be considered as data of the Acute Exacerbation Phase.

On a per patient basis, the percentage of days in the Acute Exacerbation Phase will be calculated using the following formula:

- % of days with rescue medication (Acute Exacerbation Phase) = (Number of days with rescue medication during the Acute Exacerbation Phase/Number of days with data recorded during the Acute Exacerbation Phase)*100.

Stabilisation Phase:

- Percentage of days: data recorded from the day of Visit 9/Day 14 to the day of End of Study will be considered as data of the Stabilisation Phase.

On a per patient basis, the percentage of days in the Stabilisation Phase will be calculated using the following formula:

- % of days with rescue medication (Stabilisation Phase) = (Number of days with rescue medication during the Stabilisation Phase/Number of days with data recorded during the Stabilisation Phase)*100.

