10.6 Concomitant Therapy

10.6.1 Permitted Concomitant Medication for COPD

1. Long-acting anti-histamines if taken at stable regimen at least 2 months prior to Screening or if taken PRN. For subjects not on stable, long-acting anti-histamines, short courses are allowed during the study period (≤ 7 days). Other anti-histamines are allowed during the study period for a short course (≤ 10 days) or if taken PRN
2. If required for respiratory symptoms or a COPD exacerbation:
 - Systemic corticosteroid (oral/IV/intramuscular)
 - Inhaled short-acting β_2 -agonists and/or short acting muscarinic antagonists or combination of both
 - Nebulised β_2 -agonists, anti-cholinergics and/or steroids
 - Antibiotics
 - Oxygen.
3. Mechanical ventilation at the investigator's discretion
 - Mechanical ventilation is exclusionary at Screening. However, if the subject requires mechanical ventilation during the course of the study, they should remain on the study until Week 26, even if further study drug cannot be administered or assessments carried out.
4. Short courses (≤ 10 days) of nasal corticosteroids (maximum two courses) are allowed
5. Current regular therapy for COPD as stated in inclusion criterion 8
6. Current regular theophylline.

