11 ASSESSMENT OF EFFICACY

11.1 Efficacy Variables

1. FEV1, FVC and FEV1/FVC on Days 1 to 7 (daily), 10, 14, and at Weeks 8,12 and 26
2. FEV1, FVC and FEV1/FVC form the most recent test performed within the last 12 months outside an exacerbation
3. Time to improvement of 100 mL in FEV1 compared to Baseline versus placebo
4. AUC of FEV1
5. RR on Days 1 to 7 (daily), Days 10, 14, and at Weeks 8,12 and 26
6. EXACT-PRO score daily from Baseline up to the end of subject participation
7. AUC of EXACT-PRO
8. Number of COPD-related deaths from first dose intake up to the end of study participation (Week 26)
9. Number of moderate/severe COPD exacerbations over time among groups
10. Time to next moderate/severe COPD exacerbation (in days)
11. Number of uses of rescue therapy during the study
12. Time from hospitalisation until the subject is medically ready for discharge
13. Exploratory composite endpoints:
 - Number of events of worsening of symptoms warranting the addition of antibiotics
 - Number of events of worsening of symptoms warranting an increase of oral dose of corticosteroids or initiation of new oral corticosteroids
 - Number of events of worsening of symptoms requiring additional treatment with oral corticosteroids and/or antibiotics after completion of the initial regimen
 - Number of events of COPD exacerbations that required re-hospitalisation
 - Number of COPD-related deaths.
14. CRQ scores at Baseline, Day 14 and at Weeks 8, 12 and 26
15. Cumulative oral/IV steroid dose Days 1 to 14, and from Day 14 to Week 26
16. Blood biomarkers (IL-6, TNF- α , fibrinogen, hs-CRP, and MPO)
17. BCT197 exposure on Days 1, 3, and 5
18. Body Mass Index at Baseline, Days 7, 14, and Weeks 8, 12 and 26
19. Dyspnoea (mMRC dyspnoea scale) at Baseline, Days 7, 14, and Weeks 8, 12 and 26
20. 6MWT and BMI Day 14 (for BODE index calculation).

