13.4.2 Secondary Efficacy Endpoint(s)

Efficacy will be further assessed based on the following secondary endpoints:

1. Comparison of FEV1 on Days 3, 10, and 14
2. Normalisation evaluation of spirometry parameter (FEV1, FVC and FEV1/FVC) response over time (performed from Days 1 to 7, 10, 14, and at Weeks 8, 12 and 26) compared with the most recent test performed within the last 12 months outside and exacerbation (pre-study FEV1, FVC, and FEV1/FVC value)
3. Time taken to improvement of 100 mL in FEV1 compared to Baseline versus placebo
4. Comparison of AUC of FEV1 over time among groups
5. Change in RR over time (performed daily from Days 1 to 7, 10 and 14) among groups
6. Change in RR on Days 3, 7, 10 and 14 among groups
7. Time to improvement based on EXACT-PRO total score
8. Comparison of AUC of EXACT-PRO over time among groups
9. Number of COPD-related deaths during the study

10. Number of moderate/severe COPD-related exacerbations during the study
11. Time to next moderate/severe COPD exacerbation
12. Change from Baseline at each inter-visit period and over the entire period of the study in the average EXACT-PRO total score and domain scores
13. Number of times each subject required rescue therapy during the study
14. Time from hospitalisation until the subject is medically ready (COPD-related) for discharge
15. Nonlinear mixed effects PK/PD models evaluating the relationship between BCT197 exposure and efficacy/safety endpoints.

More details and the time points for collection are given in [Section 9.1.3](#) and in the Schedule of assessments ([Table 9-1](#)). A complete list of efficacy endpoints is given in [Section 11.2](#).

These secondary efficacy parameters will be assessed using the ITT population.

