8.6.3.15 Percentage of days with intake of COPD rescue therapy

Based on ‘Rescue Medication’ form of the eCRF, a descriptive summary of the number and proportion of subjects requiring COPD rescue therapy will be provided for each visit per treatment regimen. Moreover, the COPD rescue medication category (Monotherapy: Short-Acting β 2-Agonist [SABA] alone, Short-Acting Muscarinic Antagonist [SAMA] alone, Long-Acting β 2-Agonist [LABA] alone; Dual therapy: SABA+SAMA, SABA+Inhaled Corticosteroids [ICS], LABA+ICS, LABA+SAMA, LABA+SABA; Other) will be presented for each visit per treatment regimen.

Additionally, the percentage of days with intake of COPD rescue therapy (see Section 7.1.4.12 for further details on calculation) will be summarised for each inter-visit period, for the Acute Exacerbation Phase and for the Stabilisation Phase separately, using descriptive statistics by treatment regimen.

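### The rescue-therapy endpoint is named as a count, but the SAP reports only the percentage of diary days with any puffs, with no between-arm estimate and no declaration of the change

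*SAP*

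**What the plan says.** Protocol 13.4.2 item 13 gives the endpoint as "Number of times each subject required rescue therapy during the study", and SAP 4.2 item 13 repeats it. Protocol 11.1 item 11 lists the matching variable as "Number of uses of rescue therapy during the study". Both describe a count per subject.

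SAP 7.1.4.12 derives something else: "The percentage of days with intake of rescue medications will be evaluated on the basis of the information recorded daily by the patient". The day-level rule is "A day will be considered with intake of rescue medications if the answer to the question" that follows is above 0, and the question is "How many puffs of rescue medication did you take since last evening". The percentage uses days with diary data as its denominator. It is calculated for each inter-visit period, for the Stabilisation Phase and for the acute phase, where "data recorded from Study Day 1 to the day before Visit 9/Day 14 will be considered as data of the Acute Exacerbation Phase".

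SAP 8.6.3.15 adds a second source, the eCRF rescue form, from which "a descriptive summary of the number and proportion of subjects requiring COPD rescue therapy will be provided for each visit per treatment regimen", together with the class of drug used. Everything in that section is descriptive. SAP Section 9 lists three changes from the protocol (the per-protocol definition, the added per-protocol analyses and the steroid-dose window). The rescue endpoint is not among them.

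**The concern.** The variable analysed is not the variable named. The SAP contradicts both the protocol and its own endpoint list, and a reader of Section 9 would not learn of it. A change to an exploratory endpoint, cumulative steroid dose, was declared there.

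The substitution also loses information. A patient who halves daily puffs but still uses some each day scores the same as one who does not change. If use is frequent in hospital, little room is left for the measure to separate the arms in the acute phase, when study drug is given.

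SAP 8.1.4 and 8.6.1.1 promise pairwise comparison of the regimens for efficacy data, yet none is planned for this endpoint. A named secondary endpoint would be reported without an effect estimate.

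**Working it through.** **Plan's own figures.** No rescue rate and no sample size for rescue is given. The only calculation is for FEV1 (difference 100 mL, SD 230 mL, two-sided alpha 0.05, power 80%): n = 2 × (1.960 + 0.842)² × 230² / 100² = 83.04, so 84 per arm. The t-test version needs 84.01, so 85. The total is 3 × 85 = 255, and 255 / 0.95 = 268.4, so 269, against about 270 stated. This reproduces and has no bearing on the point. The 85 per arm is used below only as the group size.

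**One-day periods.** Visits 1 to 7 fall on Days 1 to 7. An inter-visit period runs from visit i to the day before visit i+1. The six periods between those visits are therefore one day each, and a patient's percentage in them can only be 0 or 100. The acute phase has 6 × 1 + 3 (Days 7–9) + 4 (Days 10–13) = 13 diary days.

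**Simplest case.** Eight puffs every day and four puffs every day both score 100% of days. The difference is 4 puffs a day on the count and 0 on the percentage.

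**Illustration with assumed inputs.** Daily puffs are Poisson, with patient-level gamma variation of mean 1 and variance d, and 25% fewer puffs on active. The expected share of days with any use at mean m is 1 − (1 + m·d)^(−1/d). With d = 0.5 and m = 8 this is 1 − 5^(−2) = 96.0%. On active, m = 6 gives 1 − 4^(−2) = 93.75%, so a quarter fewer puffs moves the measure by 2.25 points. Power is from 1,000 simulated trials per row (Monte Carlo standard error at most 1.6 points), using two-sided 5% t-tests:

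| Placebo puffs/day | % days, placebo | % days, active | Power, total puffs | Power, % days |
|---|---|---|---|---|
| 0.5 | 36.0 | 29.1 | 61.5% | 57.5% |
| 1 | 55.6 | 47.1 | 67.2% | 56.4% |
| 2 | 75.0 | 67.3 | 69.6% | 46.8% |
| 4 | 88.9 | 84.0 | 74.5% | 38.1% |
| 8 | 96.0 | 93.8 | 73.0% | 20.9% |

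**Range over d = 0.25 to 1.0.**
- At 4 a day: total puffs 93.8% to 45.3%, percentage of days 60.4% to 20.0%.
- At 8 a day: 95.7% to 45.0%, against 30.4% to 13.6%.
- At 0.5 a day: 79.9% to 38.9%, against 75.3% to 33.7%.

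The share of power lost runs from 1 − 60.4/93.8 = 36% (4 a day, d = 0.25) to 1 − 20.9/73.0 = 71% (8 a day, d = 0.5). At 0.5 a day it is 6% to 13%.

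**Rank tests narrow the gap.** With Wilcoxon tests and d = 0.5, power is 68.8% against 49.5% at 4 a day, 64.8% against 28.2% at 8, and 53.2% against 52.2% at 0.5.

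These figures describe what each variable could show if it were tested. The SAP tests neither.

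**The case against.** Five points can be made for the plan.

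1. A once-daily diary makes days with use a defensible reading of times required, and puffs are not times either, since one use may be several puffs. This stands as a caution on the repair. It does not explain why the recorded number is discarded or why the change is undeclared.

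2. A reader might infer that the measure sits at its ceiling, or cannot show a reduction. The documents do not support that. They give no usage rate, the ceiling vanishes at low use, and even at 8 puffs a day some power remains. The acute window also includes days after discharge for patients who leave early. Frequent inpatient use is plausible, and the timing of spirometry after short-acting bronchodilator could add to it, but that is inference. It does not carry over to the Stabilisation Phase.

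3. A reader might infer that nebulised rescue is ignored, or that sicker patients are scored as non-users. Protocol 10.6.1 does permit nebulised β2-agonists, "anti-cholinergics and/or steroids", but as treatment for symptoms or an exacerbation, without labelling them rescue. Scheduled nebulisation may simply be standard of care. The eCRF rescue form is not limited to puffs. What remains is that the diary question counts puffs and the SAP does not say how a nebulised dose is entered, so the diary measure may miss it.

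4. It would be too strong to say the arms are never compared, because results are tabulated by regimen. Change in respiratory rate (SAP 8.6.3.6) is also descriptive only. The accurate statement is that no difference, interval or test is planned.

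5. This is one of 15 secondary endpoints in a Phase IIa study whose analyses the protocol calls exploratory. That is correct and limits the weight of the point.

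**Conclusion.** The point holds in this form. The named count is not derived anywhere in the SAP. It is replaced by a dichotomised diary measure and a per-visit summary of subjects needing rescue, without a between-arm estimate, and Section 9 is silent. These parts rest on the documents alone.

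The size of the information loss is conditional. Under the stated model, roughly a third to seven tenths of the count's power is lost at an assumed 4 to 8 puffs a day with t-tests, less with rank tests, and little at 0.5 a day. The restriction to 0 or 100 in the six one-day periods is structural and needs no assumption. Possible under-recording of nebulised rescue is an unspecified rule, not a demonstrated bias.

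The primary FEV1 conclusion is unaffected. The plan should still be corrected, because the information is already collected and the inconsistency is plain.

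**What to change.** In SAP 7.1.4.12 and 8.6.3.15:

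- Derive total or mean daily puffs per patient from the existing diary answer for Days 1–7, the Acute Exacerbation Phase and the Stabilisation Phase.
- Give pairwise between-regimen estimates with 95% confidence intervals, for example from a negative binomial model with log diary days as offset (Appendix F already refers to such a model), or a Wilcoxon comparison.
- State how a day with nebulised rescue is counted, using the eCRF rescue and concomitant medication forms only as far as they record it.
- Keep the percentage of days as supportive.
- Align the wording of 4.2 item 13 and list the change in Section 9, before unblinding.

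For the puff count the cost is SAP text and programming, with no new data collection. Two limits remain. Puffs are not identical to times, so the SAP should say that it is using puffs to represent the count. Nebulised use needs separate display and may not be recoverable as a number of uses, because the documents do not show that the eCRF records each one.

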7.1.4.13 Clinical treatment failure (exploratory composite endpoint)

Clinical treatment failure (CTF) is defined as a composite endpoint in which a patient meets any one of the following criteria (a medical review will be also performed to review each patient meeting these criteria because these selections can select non-CTF patients):

- Worsening of symptoms warranting the addition of another antibiotic or initiation of a new

antibiotic (Criterion 1)

- Worsening of symptoms warranting an increase in dose of oral corticosteroids or initiation of new oral corticosteroids (Criterion 2)
- Worsening of symptoms requiring additional treatment regimen of oral corticosteroids and/or antibiotics after completion of the initial regimen (Criterion 3)
- Re-hospitalisation due to worsening of COPD and requiring additional treatment during the duration of the study due to an exacerbation of respiratory symptoms (emergency room admission for longer than 24 hours will qualify as a hospitalisation) (Criterion 4)
- COPD-related death (Criterion 5).

Criterion 1: Worsening of symptoms warranting the addition of another antibiotic or initiation of a new antibiotic will be derived from the ‘Prior (Last 6 months medication) and Concomitant Medication’ form of the eCRF. The medications recorded on this form to be considered for this criterion will verify:

- Antibiotics: Anatomical Therapeutic Chemical (ATC) code ‘J01’
- Medication administered for COPD exacerbations only, i.e. with indication = ‘COPD exacerbation: current/during the study’
- Medication started after Study Day 1 (i.e. \geq Randomisation date + 1) and prior to or on completion of the initial treatment (systemic corticosteroids or antibiotics) for the current COPD exacerbation (started no longer than 24 hours before randomisation).

Criterion 2: Worsening of symptoms warranting an increase in dose of oral corticosteroids or initiation of new oral corticosteroids will be derived from the ‘Prior (Last 6 months medication) and Concomitant Medication’ form of the eCRF. The medications recorded on this form to be considered for this criterion will verify:

- Systemic corticosteroids: ATC code ‘H02’
- Route ‘PO = oral’
- Medication administered for COPD exacerbations only, i.e. with indication = ‘COPD exacerbation: current/during the study’
- Medication started after Study Day 1 (i.e. \geq Randomisation date + 1) and prior to or on completion of the initial treatment (systemic corticosteroids or antibiotics) for the current COPD exacerbation (started no longer than 24 hours before randomisation).

Criterion 3: Worsening of symptoms requiring additional treatment regimen of oral corticosteroids and/or antibiotics after completion of the initial regimen will be derived from the ‘Prior (Last 6 months medication) and Concomitant Medication’ form of the eCRF. The medications recorded on this form to be considered for this criterion will verify:

- Systemic oral corticosteroids (ATC code ‘H02’ and Route ‘PO = oral’) or Antibiotics (ATC code ‘J01’)
- Medication administered for COPD exacerbations only, i.e. with indication = ‘COPD

exacerbation: current/during the study'

- Medication started after completion of the initial treatment (systemic corticosteroids or antibiotics) for the current COPD exacerbation (started no longer than 24 hours before randomisation).

Criterion 4: Re-hospitalisation due to worsening of COPD and requiring additional treatment during the duration of the study due to an exacerbation of respiratory symptoms will be determined based on the COPD exacerbations experienced after the initial study COPD exacerbation and recorded on the 'Acute Exacerbation COPD' form of the eCRF. This criterion will verify:

- "Has the patient experienced any COPD exacerbations after the initial qualifying study exacerbation subsided?" = 'Yes'
- Treatment: Systemic corticosteroids = 'Yes' or Antibiotics = 'Yes'
- Hospitalisation = 'Yes' or (Emergency room = 'Yes' with a admission longer than 24 hours).

Criterion 5: COPD-related death will be determined based on the COPD exacerbations experienced during the study (including the initial study COPD exacerbation) and recorded on the 'Adverse Event' form of the eCRF. This criterion will verify:

- AE Preferred Term 'Chronic obstructive pulmonary disease'
- Serious AE that 'Results in death'.

The cumulative incidence of CTF as well as each of the individual criteria will be evaluated at Day 30, Day 60, Day 90, Day 120, Day 150 and Day 180.

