11.2.4 Number of COPD-related deaths

The number of COPD-related deaths will be determined at the end of the study. It is the responsibility of the investigator to define whether death was COPD-related. The rationale used in this causality assessment should be recorded in the source documents and in the eCRF.

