12.1 Adverse Events

12.1.1 Definitions

The definitions for AEs and SAEs are given below. It is of the utmost importance that all staff involved in the study are familiar with the content of this section. The principal investigator is responsible for ensuring this.

Adverse Event/Reaction

An AE is defined as any untoward medical occurrence in a subject, or clinical investigation subject administered a pharmaceutical product, and which does not necessarily have a causal relationship with this treatment. An AE can therefore be any unfavourable and unintended sign, symptom or disease temporally associated with the use of a medicinal (investigational) product, whether or not related to the medicinal (investigational) product.

Any relevant observations made at the Screening Visit (prior to signing the ICF) are to be recorded as a pre-existing condition; an AE will only be recorded if there is a worsening of the pre-existing condition during study conduct with regards to nature, severity, or frequency.

An adverse drug reaction is an “untoward and unintended response to an investigational medicinal product related to any dose administered”.

All AEs judged by either the reporting investigator or the sponsor as having a reasonable causal relationship to a medicinal product qualify as adverse reactions. The expression of “reasonable causal relationship” means to convey in general that there are facts or arguments meant to suggest a causal relationship.

Serious Adverse Event

An SAE is defined as an AE that results in one of the following outcomes:

1. Results in death

Death is not an adverse event itself, but an outcome. The cause of the death is currently the AE which resulted in death.

2. Is life-threatening

Life-threatening means that the subject was at immediate risk of death at the time of the SAE, it does not refer to a SAE that hypothetically might have caused death if it were more severe.

3. Requires in-patient hospitalisation or prolongs existing hospitalisation (This does not include prolonged hospitalisation for study purposes)

Hospitalisation is defined as at least one overnight formal admission into hospital, usually to perform additional tests, provide treatment that it is not possible to provide at

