7.1.4.14 Time to clinical treatment failure

The time to clinical treatment failure (in days) is defined as:

(Date when any one of the criteria defining the composite endpoint occurred for the first time – Date of initiation of study treatment),

where acute COPD exacerbations experienced during the study and their characteristics are recorded on the 'Acute Exacerbation COPD' form of the eCRF, i.e. in particular:

- Date of first antibiotic intake and/or first systemic corticosteroid intake for treating the COPD exacerbation
- Date of hospitalisation admission for the COPD exacerbation
- Date of emergency room admission (emergency room admission for longer than 24 hours will qualify as a hospitalisation) for the COPD exacerbation
- Date the COPD exacerbation (assessed as an AE) results in death.

Table 6: Criteria for event/censored for assessment of Time to clinical treatment failure

Situation	Date of event or Censoring	Time to clinical treatment failure	Outcome
Subjects who had any one of the criteria defining the composite endpoint	Date of clinical treatment failure after entering in study	(Time from initiation of study treatment until Date of clinical treatment failure after entering in study)	Event
Subjects who never had any one of the criteria defining the composite endpoint in study period	Withdrawal or last contact date	(Time from initiation of study treatment until Date of withdrawal or last contact date)	Censored
Subjects who died (not COPD-related)	Death date	(Time from initiation of study treatment until Date of death)	Censored
Subjects who withdrew or were lost to follow-up during the study	Withdrawal or last contact date	(Time from initiation of study treatment until Date of withdrawal or last contact date)	Censored

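### Treatment-failure Criterion 5 counts COPD-related deaths by a single adverse-event term instead of the investigator's determination that the protocol requires, so some such deaths can be missed

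*SAP*

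**What the plan says.** Protocol 11.2.4 gives the decision to one party: "It is the responsibility of the investigator to define whether death was COPD-related". It adds: "The rationale used in this causality assessment should be recorded in the source documents and in the eCRF".

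SAP 7.1.4.13, Criterion 5, uses another source. It says that "COPD-related death will be determined based on the COPD exacerbations experienced during the study (including the initial study COPD exacerbation"), as recorded on the Adverse Event form. Two conditions must hold: the "AE Preferred Term" is chronic obstructive pulmonary disease, and the event is serious with a fatal outcome. The investigator's determination is not mentioned.

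The same section adds a safeguard: "a medical review will be also performed to review each patient meeting these criteria because these selections can select non-CTF patients".

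SAP 7.1.4.14, Table 6, censors the row "Subjects who died (not COPD-related") at the date of death. SAP 8.6.4.1 reports the cumulative proportion of patients with each criterion at Days 30, 60, 90, 120, 150 and 180, and compares the regimens at each time.

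SAP section 9 lists three changes from the protocol: the per-protocol definition, the added per-protocol analyses, and the window for cumulative steroid dose. The definition of COPD-related death is not among them.

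**The concern.** The protocol and the SAP can give different answers for the same death. The protocol asks whether the investigator considers the death COPD-related. Criterion 5 asks whether the fatal adverse event was coded to one MedDRA term. If an investigator answers yes for a death whose fatal event is coded as respiratory failure or pneumonia, the protocol counts it and Criterion 5 does not.

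Death is the most severe component of the composite, and Criterion 5 is tabulated and tested by itself. Where no other criterion was met, a missed death also makes the patient a censored observation in the time-to-failure analysis. The change of definition is undeclared, so a reader of the results would not know that the deaths reported under Criterion 5 are not those the protocol defines.

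**Working it through.** No plan figure bears on this point. It is settled by setting the sections side by side.

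**Step 1: can the two rules disagree?** Protocol 12.1.1 treats death as an outcome and says: "The cause of the death is currently the AE which resulted in death". One fatal event therefore carries one term. Protocol 12.1.7 makes pneumonia a separately reported event of special interest, so a fatal pneumonia would be entered under its own term. Nothing stops an investigator from also judging that death COPD-related under 11.2.4. The rules can disagree; how often is not stated.

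**Step 2: does another provision restore the missed death?**
- *Medical review, SAP 7.1.4.13.* Its scope is "a medical review will be also performed to review each patient meeting these criteria". It can remove a patient wrongly selected. It does not examine a patient who was not selected.
- *Adjudication committee, Protocol 12.9 and SAP 8.8.1.* It reviews new exacerbations and hospitalisations for them. Neither section gives it the COPD-relatedness of deaths.
- *Secondary endpoint, SAP 8.6.3.11 and 8.6.3.12.* This uses a third rule: the fatal seriousness box on the Acute Exacerbation COPD form, with no Preferred Term filter. It does not feed Criterion 5 and does not refer to the 11.2.4 determination either.

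**Step 3: what is lost?**
- *Criterion 5 alone:* every death on which the rules disagree in this direction, at each reporting time from the death onward.
- *Composite:* only if Criteria 1 to 4 are also unmet. One possible route is death during the index admission after intravenous steroid escalation alone. Criterion 1 needs an antibiotic started after Study Day 1. Criterion 2 needs the oral route. Criterion 3 needs an oral steroid or antibiotic after the initial course. Criterion 4 needs an exacerbation after the index one.
- *Time to failure:* that same patient has no event row in Table 6. Whether placed with patients who met no criterion or with non-COPD deaths, the outcome is censored.

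**Step 4: size.** The documents give neither a COPD death rate nor the share of such deaths that the term would capture. The following is illustration only; both inputs in each row are assumptions.

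Missed deaths = COPD-related deaths × share coded to another term.

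| Assumed deaths in 270 | Assumed share missed | Missed |
|---|---|---|
| 3 | 30% | 3 × 0.30 = 0.9 |
| 8 | 60% | 8 × 0.60 = 4.8 |
| 270 × 3% = 8.1 | 25% | 8.1 × 0.25 = 2.0 |
| 270 × 8% = 21.6 | 50% | 21.6 × 0.50 = 10.8 |

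The spread, from about 1 to about 11, shows that no count can be defended. The sample size is not involved, because it rests on FEV1.

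**The case against.** The strongest reply is that the investigator is not bypassed. Entering a fatal COPD event on the Adverse Event form is itself an investigator's judgement, and Protocol 12.1.1 asks for the cause of death, not the mode of dying. Read plainly, a site that believes COPD caused the death should enter COPD, and the two rules would then usually agree. This stands as an argument about frequency. A reader might infer that sites will often enter the terminal event; the documents do not say so. It does not remove the mismatch, because the explicit determination required by 11.2.4 is still unused.

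Other stronger readings also fail:
- *That a missed death means the patient is not a treatment failure.* Any one criterion is enough, so a patient with an earlier added antibiotic, oral steroid or re-hospitalisation remains a failure and an event.
- *That the death reported in Protocol 7.1 shows how COPD deaths are coded.* That death, from respiratory failure, sepsis and multi-organ failure, occurred in the acute kidney injury study in cardiac-surgery patients. It says nothing about coding of COPD-related deaths.
- *That the secondary death endpoint is under-counted by the term rule.* It has no such filter. The two counts may differ; they need not.
- *That a coded yes/no field is already available.* Protocol 11.2.4 requires the rationale in the eCRF. It does not promise a discrete variable.

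It is also fair to say that the composite is exploratory and that Protocol 13.5.1 treats all analyses as exploratory, without multiplicity adjustment.

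**Conclusion.** The point holds for Criterion 5. The SAP replaces a determination that the protocol assigns to the investigator with a coding rule, does not declare the change, and provides a review that works in one direction only. The consequence is certain for the Criterion 5 table and tests whenever the two rules disagree in this way. For the composite and the time-to-failure analysis it is conditional on Criteria 1 to 4 being unmet.

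The number of deaths affected is unknown and could be zero; the conclusion does not rest on the illustrative counts. The reach is limited to an exploratory endpoint and does not touch the primary analysis or the sample size. The change should be made because it concerns the gravest component of the composite and costs little.

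**What to change.** - Define Criterion 5 as any death the investigator determined to be COPD-related under Protocol 11.2.4, whatever the Preferred Term. SAP 7.1.4.14 already dates a fatal failure at the death, and that can stay.
- Apply the same determination to the Table 6 row for deaths that are not COPD-related.
- Keep the Preferred Term rule as a consistency check, and list the deaths on which the two disagree.
- Confirm what the eCRF holds. If it holds only the free-text rationale, extend the blinded medical review to all deaths and classify each from that rationale before database lock.
- Use the same determination for the secondary endpoint in SAP 8.6.3.11 and 8.6.3.12, or list any remaining departure in section 9.

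The cost is SAP wording and, if no coded field exists, a blinded review of what is likely to be a small number of deaths.
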